9.7 End of Study Definition

The study will continue until data on all randomised patient episodes have been collected (including 28 days follow-up) or on completion of the 36-month period taken from time of first patient randomized. Patients will be enrolled until the end of study or until they have been treated for up to two pain episodes within the trial protocol.

9.8 Procedures for unblinding

Not applicable

9.9 Subject Withdrawal

Subjects can be withdrawn at any stage after giving consent. They should contact a trial or clinical staff member and indicate that they no longer wish to participate. This is the case whether or not they have participated in the trial during a previous APC event .

9.10 Data Collection and Follow up for Withdrawn Subjects

A first APC treated in on trial can be used for data analysis if a patient subsequently withdraws consent from continuing in the trial for a second episode.

10. Assessment and management of risk

No investigational medicinal product is being used in this trial. The analgesic drugs and any non-pharmacological agents used to treat pain will be the same as in their standard care protocol. Observations and any bloods tests or diagnostic imaging will be performed as required for standard of care, and will not be part of the trial evaluation. Subjects who would normally access ACU for their care may be randomised to ED care, and this may be perceived by the subject as a worse option. The risks for subjects involved in the study include:

- Trial procedures delaying access to standard care.
- Trial procedures interfering with standard care and with teams implementing. standard protocols in acute care and, for those admitted to hospital, after admission to medical wards.
- Patients being discharged from hospital and not followed up according to standard care protocols once discharged.

In mitigation, both treatment arms incorporate measures to improve on current standard of care during the initial stages of hospital management of acute pain. These include allocation of individualised care plans in both arms of the study (treatment in ED or on ACU), enhanced supervision of the trial subjects, which is anticipated to improve patient safety and satisfaction and reduce harm. Prior to implementation of the trial in trial centres, and during the trial implementation period, there will be regular

training sessions for clinical trial staff and standard care staff, to ensure that trial procedures are correctly implemented.

There will also be an independent trial monitoring committee which will evaluate safety and operational problems during the entire clinical trial implementation period.

11. Statistical considerations

11.1 Sample size

The target sample size is 228 patient episodes (114 per group). This provides 90% power (with 2-sided α =0.05) to detect a mean difference between ambulatory care and hospital emergency department of 1.3 in pain scores on a 0-10 visual analogue scale at 6 hours after presentation. A difference of 1.3 in pain scores has been used as a clinically important difference in other studies.^{9, 19} Data from the SCAPE trial provided an estimate of 3.2 for the standard deviation (SD) for pain scores and informed a conservative estimate of the correlation between baseline and 6-hour pain scores of 0.5¹⁸. The sample size allows for a conservative 15% dropout by 6 hours, informed by data from the SCAPE trial. It is anticipated that dropout will be minimised by potential use of an app to collect data including pain scores.

11.2 Method of analysis

Baseline characteristics will be summarised for each randomised group using descriptive statistics.

Pain scores at each time-point will be described for each randomised group using mean (SD), or median (interquartile range, IQR) if distributions are skewed. The primary outcome of pain score over the 6 hours following presentation will be compared between randomised groups using a longitudinal mixed linear regression model that includes all timepoints from baseline, and at each hour up to 6 hours after presentation. Performing a longitudinal analysis of all time-points using all non-missing data should allow for greater precision in the estimation of treatment effect specifically at 6 hours (the primary outcome) than an analysis of this time-point alone. The model will include fixed effects for intervention (ACU versus ED) and for the stratification factors age and previous history of acute pain crises, with random effects for site, timepoint and APC. The treatment effect of ACU versus ED will be summarised by an adjusted mean difference in pain scores with a 95% confidence interval, and significance assessed using the Wald test.

The mixed-effects model assumes that data are missing at random, i.e. results are unbiased if missingness is related to observed outcome data or stratification factors from the same participant. Patterns of missingness in the primary outcome data will be examined and a sensitivity analysis will estimate the treatment effect with missing data imputed.

The unit of randomisation is an APC, and participants may be randomised more than once within the trial. Previous studies have not shown evidence of clustering within participants in terms of outcomes for separate episodes¹⁸, but this will be tested for in a sensitivity analysis for the primary outcome by including a random effect for participant in the regression model.

Secondary outcomes will be compared between randomised groups using methods appropriate for the type of data.

Analyses will be done on an intention-to-treat basis, including all participants according to randomised allocation.

Data collected from participants in the observational cohort will be summarised separately from those randomised into the trial using descriptive statistics.

Full details of analyses will be described in a separate Statistical Analysis Plan.

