Statistical methodology and analysis (if applicable)	The primary outcome of pain score over the 6 hours following presentation will be compared between randomised groups using a mixed effects regression model accounting for correlation between repeated observations within participants. Analyses will be done on an intention-to-treat basis.
Study duration	36 months

5. Introduction

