6.3 Primary endpoint

• Reduction in pain score during the first 6 hours after presentation to ED and ACU using a 0-10 numeric rating scale.

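### The primary model listed in Section 11.2 estimates an average ACU-ED difference over hours 0 to 6, not the 6-hour difference that 11.1 powers and 11.2 calls primary

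*Protocol*

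**What the plan says.** **Target.** Section 11.1 plans to detect a difference "of 1.3 in pain scores on a 0-10 visual analogue scale at 6 hours after presentation". Section 11.2 justifies a longitudinal analysis by its precision for the "estimation of treatment effect specifically at 6 hours (the primary outcome"). Other places word the target as a period. Section 6.3 has "Reduction in pain score during the first 6 hours after presentation to ED and ACU using a 0-10 numeric rating scale", and both the synopsis and Section 11.2 have "The primary outcome of pain score over the 6 hours following presentation". The assessment of outcomes in 11.3.1 also refers to pain during the first 6 hours.

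**Model.** Section 11.2 specifies "a longitudinal mixed linear regression model that includes all timepoints from baseline" and then hourly to 6 hours. Of the terms, "The model will include fixed effects for intervention (ACU versus ED) and for the stratification factors age and previous history of acute pain crises", with site, timepoint and APC as random effects. No fixed effect of hour, intervention-by-hour term or baseline covariate is listed. The result is to be one adjusted mean difference with a 95% confidence interval and a Wald test, with no hour named.

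**Size.** "The target sample size is 228 patient episodes (114 per group"). "This provides 90% power (with 2-sided α =0.05) to detect a mean difference" of 1.3, using SD 3.2, a baseline to 6-hour correlation of 0.5 and 15% dropout by 6 hours.

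**The concern.** A model with one intervention main effect assumes that the mean gap between ACU and ED is the same at every time in the outcome vector. Here that vector includes the score on arrival, before the unit has given any care, and a gap produced by care must start near zero and develop. The fitted coefficient then averages the hourly gaps and is a different quantity from the gap at 6 hours.

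Three consequences follow. The reported difference cannot be set against the 1.3-point benchmark. The 90% power was computed for an analysis that the listed model does not perform. The test can also err in either direction about hour 6: it can miss a real 6-hour difference that builds slowly, or be significant when an early difference has gone by hour 6.

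**Working it through.** **Inputs from the protocol (11.1):** difference 1.3, SD 3.2, correlation 0.5, two-sided alpha 0.05, power 90%, dropout 15%, 114 per group.

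**Step 1: reproduce the sample size.** Baseline-adjusted comparison at 6 hours:

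n = 2 × (1.96 + 1.2816)² × 3.2² × (1 − 0.5²) / 1.3² = 95.5 per arm.

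The noncentral-t version needs 97, and 97 / 0.85 = 114.1, which matches the stated 114. Without the factor (1 − 0.5²), n is 128 per arm, or 151 after dropout. A change score at equal SDs and correlation 0.5 also needs 128. So 114 fits only a baseline-adjusted comparison at hour 6.

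**Step 2: what the listed model estimates.** On complete data, with random intercepts for timepoint and APC, every episode contributes the same seven times. The intervention coefficient is therefore the difference between arms in the episode means:

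coefficient = (d0 + d1 + … + d6) / 7, where dk is the ACU-ED difference at hour k.

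With d0 = 0 and a constant difference of 1.3 from hour 1, this is 1.3 × 6/7 = 1.11.

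**Step 3: its standard error.** Assumed: 97 complete episodes per arm.

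- Exchangeable correlation 0.5: SE = √[2 × 3.2² × (1 + 6 × 0.5) / 7 / 97] = 0.347.
- AR(1), with baseline to 6-hour correlation 0.5: SD of the seven-time mean 2.829, so SE = 2.829 × √(2/97) = 0.406.

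**Step 4: power** = Φ(coefficient / SE − 1.96). The effect profiles are assumptions; the protocol gives none.

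| Assumed profile | True difference at 6 h | Coefficient | Power, exchangeable | Power, AR(1) |
|---|---|---|---|---|
| Full from hour 1 | 1.3 | 1.11 | 89% | 78% |
| Linear to hour 3, then flat | 1.3 | 0.93 | 76% | 63% |
| Linear from 0 to 6 h | 1.3 | 0.65 | 46% | 36% |
| Nil to hour 3, then linear | 1.3 | 0.37 | 19% | 15% |
| 1.3 at hours 1 to 3, fading to nil at 6 h | 0 | 0.74 | 57% | 45% |

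The baseline-adjusted 6-hour contrast has Φ(1.3 / [3.2 × √0.75 × √(2/97)] − 1.96) = 90% in each of the first four rows.

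**Step 5: simulation check** (linear build, exchangeable, 97 complete per arm, 200 runs). The main-effect model gave a mean estimate of 0.65 and rejected in 50% of runs. A model with intervention-by-hour terms gave 1.33 at hour 6 and rejected in 90%. Hour was coded as fixed in both, which does not change the main-effect coefficient on complete data. The second model used a common baseline mean, which was true by construction in the simulation.

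**The case against.** **The details belong in the SAP.** Section 11.2 defers full details to a separate plan, and saying that the model will include certain terms does not make the list exhaustive. A SAP could add the interaction. This lowers the certainty about what will finally be fitted. It does not remove the mismatch: the protocol chose to list terms, and a SAP that follows the list misses the outcome named in the same paragraph.

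**A period average may be intended.** The synopsis, 6.3, the opening of the model description in 11.2 and the assessment of outcomes in 11.3.1 all point that way, and on that reading an early benefit is a legitimate success. This stands: a reader might infer that hour 6 must be primary, but the documents support only that the target be reconciled. Baseline should still not be averaged in, and the power statement does not carry over. For a baseline-adjusted mean of hours 1 to 6 under exchangeable correlation, SE = √{2 × 3.2² × [(1 + 5 × 0.5)/6 − 0.5²] / 97} = 0.265. A linear build gives a mean of 0.76 and power of 82%; a plateau at hour 3 gives 1.08 and 98%.

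**The losses rest on chosen profiles.** True. If the effect is complete by hour 1 and correlation is exchangeable, almost no power is lost. Nor is the coefficient always pulled towards zero relative to the 6-hour effect: in the fading profile it exceeds it.

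**Random timepoint might rescue the contrast.** It does not, because neither a random intercept by hour nor a random slope per episode lets the mean ACU-ED gap vary with time. Under a random slope the weighting of hours depends on variances that the protocol does not give, so no figure is offered for that reading.

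**Baseline is measured after randomisation.** Randomisation is by telephone (9.4), the first score is taken in ED or ACU (Table 1 in 9.6), the trial is open, and 6.4 foresees parenteral opioid in the ambulance. Equal baseline means are therefore not guaranteed by design. This limits the choice of remedy.

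**Conclusion.** The point holds and should be corrected. Section 11.2 names one quantity as primary and lists a model that estimates another. With timepoint as a random intercept and complete data, the coefficient is the 0 to 6 hour average. For a difference that is nil on arrival and never exceeds 1.3, it is at most 1.11.

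Across profiles that all reach 1.3 at hour 6, power runs from 89% to 19% under exchangeable correlation and from 78% to 15% under AR(1), against 90% for the contrast that 11.1 sized. A benefit that is nil at hour 6 could be significant in 57% or 45% of trials. These figures rest on assumed profiles, assumed correlation structures and 97 complete episodes per arm; only SD 3.2 and the 0.5 correlation come from the protocol.

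A reader might go further and infer that the sample size is wrong or that the trial has 46% power. The documents support neither. The 114 per group reproduces, and 46% belongs to one assumed profile under the listed model.

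**What to change.** Use one target in the synopsis, 6.3, 11.1, 11.2 and 11.3.1.

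- **If the target is pain at 6 hours** (the one that 11.1 powers): add fixed effects for categorical hour and intervention-by-hour, take hours 1 to 6 as outcomes with the baseline score as a covariate, report the ACU-ED contrast at hour 6 as primary, and make the average over hours 1 to 6 secondary. The 114 per group stands.
- **If the target is the average:** define it over hours 1 to 6, leave baseline out of the average, and re-justify both the 1.3-point difference and the stated power for that quantity.

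Because baseline is scored on arrival after randomisation, do not constrain the baseline means to be equal without a justification. Add a sensitivity analysis without baseline adjustment; at hour 6 with 97 per arm its power is Φ(1.3 / [3.2 × √(2/97)] − 1.96) = 81%, so it serves as support and not as a replacement.

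For the 6-hour target the cost is wording in five places and a few more model parameters, with no extra patients or data. For the average it also includes a new sample size justification. The differing names for the 0 to 10 pain scale are a separate editorial correction.

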11.3.1 Analysis of cost-effectiveness

Within-trial cost-effectiveness of ambulatory care management of acute sickle cell painful crises

For a within trial evaluation, incremental costs and outcomes between the two treatment arms will be compared and an incremental cost-effectiveness ratio (ICER)

will be estimated. Given the two outcomes, additional cost per unit of pain decreased within 6 hours and the additional cost per QALY gained will be estimated. We will assess uncertainty around the ICER using nonparametric bootstrapping with replacement by treatment allocation. The probability of the intervention being cost-effective compared to current usual care will be reported across cost-effectiveness thresholds ranging from 0 to £30,000/QALY gained.²⁰

Cost-effectiveness of ambulatory care management of acute sickle cell pain episodes: impact of prevalence and ambulatory unit size and opening hours

In addition to the within trial evaluation, we will assess the value of wider adoption of the ambulatory care model. The main question the model-based evaluation will address is what is the cost-effectiveness of the ambulatory unit care pathway depending on ambulatory unit size and service configurations and prevalence of sickle cell patients in the area, and over a longer time horizon beyond the 14 days follow-up in the trial. The impact of unit sizes, configuration and demand on cost and costeffectiveness of the new model of care will be assessed. We will develop a Markov model with 10 year time horizon and an annual cycle length. In the ED only care setting, we will assume patients who seek treatment for acute pain episodes will have access only to ED and will be in one of the two states after treatment in ED: hospitalised or discharged. On the other hand, patients with access to ambulatory units will be able to access treatment via ED or ambulatory units. We will assume those treated via ED may transition to being hospitalised, discharged or transferred to ambulatory units. Similarly, those treated via ambulatory units may transition to hospital admission or discharged. We will estimate the transition probabilities between different states using trial data. We will complement trial data with additional data drawing from relevant literature and reports³² as well as extracts of further data from study centres.

12. Ethics

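### Participants may be randomised for two episodes, but the primary model leaves participant to a sensitivity analysis; this gives up precision, by an amount that depends on an unstated correlation, without harming validity

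*Protocol*

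**What the plan says.** Section 11.2 makes the APC the unit of randomisation and allows a participant to be randomised more than once. The exclusion criteria in section 7.2 cap this at two episodes, at least 28 days apart, and section 9.7 keeps patients enrolled "until they have been treated for up to two pain episodes within the trial protocol". Section 9.4 randomises 1:1, stratified by site, APC history and age, so a participant's second allocation is not tied to the first.

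The primary model in section 11.2 is a longitudinal mixed model "with random effects for site, timepoint and APC". Participant enters only as a secondary check: "this will be tested for in a sensitivity analysis for the primary outcome by including a random effect for participant in the regression model". The reason given is that clustering within participants was not evident in previous work. One reference is cited for this, which section 5.1 describes as a dose-finding and feasibility study at one hospital.

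The synopsis describes the primary comparison as "using a mixed effects regression model accounting for correlation between repeated observations within participants".

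Section 11.1 counts episodes: "The target sample size is 228 patient episodes (114 per group"), with no allowance for two episodes coming from one person. In the cost-effectiveness analysis of section 11.3, "We will assess uncertainty around the ICER using nonparametric bootstrapping with replacement by treatment allocation"; the resampling unit is not named.

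**The concern.** With up to two episodes per person, participant and APC are different levels. An APC effect ties together the hourly scores of one episode but treats a person's two episodes as unrelated. Some correlation is plausible, because each participant is treated under a personal pain protocol that applies to both episodes. Failure to detect clustering in one earlier study is weak support for independence, and the protocol reports no intraclass correlation.

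At stake is how efficiently the treatment effect is estimated. When a person has one episode in each arm, the two scores give a within-person comparison, and a model without a participant level does not use it. There is also a reporting issue: if the two pre-specified models differ, the one that follows the design's structure would be the secondary result.

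**Working it through.** **1. The plan's own figure.** Inputs from section 11.1: difference 1.3, SD 3.2, baseline to 6-hour correlation 0.5, 15% dropout. "This provides 90% power" is stated, "with 2-sided α =0.05".
- Baseline-adjusted SD = 3.2 × √(1 − 0.5²) = 2.771 (variance 7.68).
- Episodes per arm = 2 × [2.771 × (1.960 + 1.282) / 1.3]² = 95.5, so 96. With the noncentral t it is 97.
- After dropout: 96 / 0.85 = 112.9, or 97 / 0.85 = 114.1 per arm, against 114 stated. The figure reproduces, with every episode treated as independent.
- Evaluable episodes: 228 × 0.85 = 193.8, about 194.

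**2. Assumptions the protocol does not supply.** The correlation ρ between a person's two baseline-adjusted scores is varied from 0.1 to 0.5. The number k of participants with two evaluable episodes is varied from 20 to 97 (97 means that everyone repeats). The check uses the 6-hour score alone and takes ρ as known.

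**3. Variance without a participant effect.** Each episode is allocated separately, so pairs in the same arm (which raise the variance) and split pairs (which lower it) balance on average. The variance stays close to 4σ²/194, which is what a model that ignores pairing reports. The standard error is therefore right on average.

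**4. Variance with a participant effect.** Code treatment ±½. A single episode contributes information 1/4 (in units of 1/σ²). A pair contributes on average (1/2)/(1 − ρ²), against 1/2 when ρ is ignored. With s = 2k/194 the share of episodes that belong to pairs:

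variance ratio (without / with participant) = 1 + s × ρ²/(1 − ρ²)

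| ρ | ρ²/(1 − ρ²) | k = 20 (s = 0.206) | k = 40 (s = 0.412) | k = 97 (s = 1) |
|---|---|---|---|---|
| 0.1 | 0.010 | 1.002 | 1.004 | 1.010 |
| 0.2 | 0.042 | 1.009 | 1.017 | 1.042 |
| 0.3 | 0.099 | 1.020 | 1.041 | 1.099 |
| 0.5 | 0.333 | 1.069 | 1.137 | 1.333 |

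Simulated trials with 194 episodes, each randomised separately, agree within simulation error: excess variance of about 0-1%, 1-5%, 1-10% and 6-35% at the four correlations.

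**5. Error rate and power.** In those simulations the type I error was about 4.5-6% with or without participant weighting. In a further set with ρ of 0.3 to 0.5 and 50-100% of participants repeating, the error without participant was 4.5-5.4%. Power for the 1.3-point difference was 0.89-0.90 without participant and 0.92-0.96 with it. So 228 episodes suffice either way.

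**6. Bootstrap.** Over three settings of the same kind (228 episodes), resampling episodes within arm gave an average standard error of 0.131 SD units. Resampling whole participants gave 0.130-0.132. Coverage was 0.94-0.96 for both.

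**The case against.** The strongest defence is that the protocol already sees the issue, gives a reason, and pre-specifies the very model asked for, so the change only swaps which is primary and which is the sensitivity analysis. That is largely fair. The cited study is not available here, and no figure in the document shows that episodes do correlate. At correlations of 0.2 or less the gain is at most about 5%. Episodes must also meet the ACU opening-hours, staffing and 28-day limits, so universal repeats are unlikely. It remains true that non-detection in one study does not establish independence, and that the swap costs nothing.

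Four stronger readings are tempting, and the document does not support them.
- **Inflated false positives or too small a sample.** Design-effect reasoning suggests this, but it applies when both episodes of a person fall in the same arm by design. Here they are allocated separately. At correlation 0.5 the error reaches 6-7% only if about 65% of pairs happen to share an arm. The binomial probability of that is about 4% with 40 pairs (26 or more) and 0.1% with 97 (64 or more).
- **A contradiction with the synopsis.** Its phrase can be read as the hourly scores within one episode, which the APC effect covers. It is loose wording that should be aligned.
- **A faulty bootstrap.** Resampling by arm cannot keep together a participant with one episode in each arm, but the unit is not stated and the expected effect is negligible.
- **Missing participant effects for secondary outcomes.** Those models are properly left to the SAP.

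**Conclusion.** The point holds as a matter of efficiency. Section 11.2 fixes a primary model that omits a level the design creates, on thin evidence that the level does not matter. Inference stays valid on average and the sample size stands. The cost is forgone precision: negligible at correlation 0.1, at most about 5% of variance at 0.2 and about 10% at 0.3, and 6-35% at 0.5. The 35% needs both a correlation of 0.5 and two evaluable episodes from every participant. These sizes rest on the assumed correlations and repeat shares, on 194 evaluable episodes, on separate allocation of each episode, and on a correlation treated as known; estimating it from few pairs would recover somewhat less. It is a modest improvement available at no cost, and worth making before any results are seen.

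**What to change.** - In section 11.2, put a participant random intercept in the primary model with APC nested within participant, and make the model without participant the sensitivity analysis.
- In the synopsis, name both levels, so that its reference to participants matches section 11.2.
- Optionally, for consistency, state in section 11.3 that the bootstrap resamples participants with all their episodes. Little change in the results should be expected.

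The cost is a line of text in each place. No extra patients, data or sample-size revision are needed. If the participant variance is estimated as zero, the primary result is the same as under the current model.
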